8.11. Occupational Exposure

An occupational exposure occurs when, during the performance of job duties, a person (whether a healthcare professional or otherwise) gets in unplanned direct contact with the product, which may or may not lead to the occurrence of an AE.

An occupational exposure is reported to the drug safety unit within 24 hours of the investigator's awareness, using the SAE report form, regardless of whether there is an associated AE/SAE. Since the information does not pertain to a patient enrolled in the study, the information is not reported on a CRF; however, a copy of the completed SAE report form is maintained in the investigator site file.

8.12. Withdrawal Due to Adverse Events (also see [Section 6.5 Patient Withdrawal](#))

Withdrawal due to AEs should be distinguished from withdrawal due to other causes, according to the definition of AE noted earlier, and recorded on the appropriate AE CRF page.

When a patient withdraws because of an SAE, the SAE must be reported in accordance with the reporting requirements defined below.

8.13. Eliciting Adverse Event Information

The investigator is to report all directly observed AEs and all AEs spontaneously reported by the study patient or legally acceptable representative. In addition, each study patient or legally acceptable representative will be questioned about AEs.

8.14. Reporting Requirements

Each AE is to be assessed to determine if it meets the criteria for SAEs. If an SAE occurs, expedited reporting will follow local and international regulations, as appropriate.

8.14.1. Serious Adverse Event Reporting Requirements

If an SAE occurs, Pfizer is to be notified within 24 hours of investigator awareness of the event. In particular, if the SAE is fatal or life-threatening, notification to Pfizer must be made immediately, irrespective of the extent of available AE information. This timeframe also applies to additional new information (follow-up) on previously forwarded SAE reports as well as to the initial and follow-up reporting of EDP, exposure via breastfeeding, and occupational exposure cases.

In the rare event that the investigator does not become aware of the occurrence of an SAE immediately (eg, if an outpatient study patient initially seeks treatment elsewhere), the investigator is to report the event within 24 hours after learning of it and document the time of his or her first awareness of the AE.

For all SAEs, the investigator is obligated to pursue and provide information to Pfizer in accordance with the timeframes for reporting specified above. In addition, an investigator may be requested by Pfizer to obtain specific additional follow-up information in an expedited fashion. This information collected for SAEs is more detailed than that captured on the AE CRF. In general, this will include a description of the AE in sufficient detail to allow for a complete medical assessment of the case and independent determination of possible causality. Information on other possible causes of the event, such as concomitant medications, vaccines, and/or illnesses must be provided. In the case of a patient death, a summary of available autopsy escalations must be submitted as soon as possible to Pfizer or its designated representative.

8.14.2. Non-Serious Adverse Event Reporting Requirements

All AEs will be reported on the AE page(s) of the CRF. It should be noted that the form for collection of SAE information is not the same as the AE CRF. Where the same data are collected, the forms must be completed in a consistent manner. For example, the same AE term should be used on both forms. AEs should be reported using concise medical terminology on the CRFs as well as on the form for collection of SAE information.

For Investigative Sites in Japan Only:

After avelumab is approved for treatment of advanced urothelial carcinoma by the Ministry of Health, Labour and Welfare (MHLW) in Japan, investigators in Japan may be requested by Pfizer to obtain specific additional follow-up information to be provided to Pharmaceuticals and Medical Devices Agency (PMDA) and/or MHLW if a reported treatment-related non-serious AE is found to be unexpected according to the Japanese Prescribing Information. If this occurs, the investigator will be required to pursue and provide the additional information to Pfizer; this information may be more detailed than the information captured on the adverse event case report form. In general, the information will include sufficient detail regarding the description of the adverse event to allow for a complete medical assessment of the case and independent determination of possible causality. Information regarding other possible causes of the adverse event, such as concomitant medications and illnesses, must also be provided.

8.14.3. Sponsor's Reporting Requirements to Regulatory Authorities

Adverse event reporting, including suspected unexpected serious adverse reactions, will be carried out in accordance with applicable local regulations.

9. DATA ANALYSIS/STATISTICAL METHODS

Detailed methodology for summary and statistical analyses of the data collected in this study will be documented in a statistical analysis plan (SAP), which will be maintained by Pfizer. This document may modify the plans outlined in the protocol; however, any major modifications of the primary endpoint and/or its analysis will also be reflected in a protocol amendment.

9.1. Sample Size Determination

The primary objective of this study is to demonstrate the benefit of maintenance treatment with avelumab plus BSC vs. BSC alone in prolonging OS in patients with unresectable locally advanced or metastatic UC whose disease did not progress on or following completion of first-line platinum-containing chemotherapy in each co-primary UC patient populations: 1) patients determined to have PD-L1-positive tumors (including infiltrating immune cells) by a verified GMP PD-L1 IHC test, and 2) all randomized patients.

The study will randomize a total of approximately 668 patients, with at least 334 patients with confirmed PD-L1-positive tumors, using 1:1 randomization, stratified by best response to chemotherapy (CR/PR vs. SD) and site of metastasis (visceral vs. non-visceral) at time of initiating first-line chemotherapy. The “non-visceral” stratum includes patients with locally-advanced disease as well as patients with only non-visceral disease. The type 1 error rate will be split between the co-primary populations to preserve the overall type 1 error rate for the study at 0.025 one-sided. It is estimated that at least 50% of the randomized patients will have adequate tissue for analysis and be determined to have PD-L1-positive tumors.

The sample size for this study is determined based on the following assumptions:

- For all patients and patients with PD-L1-positive tumors receiving BSC alone after first-line chemotherapy, the median OS is 12 months.³³
- For all patients receiving avelumab plus BSC after first-line chemotherapy, the median OS is assumed to be 17.1 months.
- For patients with PD-L1-positive tumors receiving avelumab plus BSC after first-line chemotherapy, the median OS is assumed to be 18.5 months.

This corresponds to a hazard ratio (HR) of 0.7 for all patients and 0.65 for patients with PD-L1-positive tumors under the exponential model assumption.

For all patients, if the true HR is 0.7 under the alternative hypothesis, a total of 425 OS events will be required to have 93% power to detect a HR of 0.7 using a one-sided log rank test at a significance level of 0.015 and a 2-look group-sequential design with Lan-DeMets (O’Brien-Fleming)⁷¹ α -spending function to determine the efficacy boundary and a Gamma Family (-8) β -spending function to determine the non-binding futility boundary.

For patients with PD-L1 positive tumors, if the true HR is 0.65 under the alternative hypothesis, then a total of 219 OS events will be required to have 80% power to detect a HR of 0.65 using a one-sided log rank test at a significance level of 0.01 and a 2-look group sequential design with Lan-DeMets (O’Brien-Fleming) α -spending function to determine the efficacy boundary and a Gamma Family (-8) β -spending function to determine the non-binding futility boundary (see [Section 9.6 Interim Analysis](#) for details).

The sample size further assumes a 5% drop-out rate for OS on either treatment arm, a non-uniform patient accrual accomplished over a 28-month period, and follow-up for about

11 months after the last patient is randomized. The data cutoff for the primary OS analysis will occur after the target number of events has been reached in both co-primary populations and the last patient randomized in the study has been followed for at least 12 months after randomization.

The study will be considered positive if the stratified log rank test for OS is significant at the respective adjusted levels at the interim or at the final analyses, for either of the two co-primary populations.

9.2. Analysis Populations

9.2.1. Full Analysis Set

The Full Analysis Set will include patients who are randomized. Patients will be classified according to the treatment and stratum assigned at randomization. The Full Analysis Set will be the primary analysis set for evaluating all efficacy endpoints and patient characteristics within each of the co-primary populations: 1) patients determined to have PD-L1-positive tumors (including infiltrating immune cells) by a verified GMP PD-L1 IHC test and 2) all randomized patients.

Patients to be included in the co-primary population defined by PD-L1 positive tumors will be determined by retrospective analysis of the mandatory recent FFPE tumor biospecimen (see [Sections 4.1](#) and [6.1.1](#)) using an analytically-validated and GMP-verified PD-L1 IHC assay with a pre-specified scoring algorithm defining PD-L1 positive status. The PD-L1 IHC assay and scoring algorithm will be fully defined prior to initiation of sample analysis.

9.2.2. Per-Protocol Analysis Set

The Per-Protocol Analysis Set is a subset of the Full Analysis Set and will include patients who receive at least 1 dose of study treatment or who only receive BSC and do not have major protocol deviations expected to impact the primary objectives of the study. Major protocol deviations will be pre-specified in the SAP. The Per-Protocol Analysis Set will be used for sensitivity analyses for the primary efficacy endpoint.

9.2.3. Safety Analysis Set

The Safety Analysis Set will include all patients who receive at least 1 dose of avelumab or who only receive BSC. Patients will be classified according to the treatment assigned at randomization unless the incorrect treatment(s) are received throughout the dosing period in which case patients will be classified according to the first treatment received. The Safety Analysis Set will be the primary population for evaluating treatment administration/compliance and safety.

9.2.4. PK Analysis Set

The PK Concentration Analysis Set will include all treated patients who have at least 1 concentration above the below limit of quantitation (BLQ) of avelumab.

The PK Parameter Analysis Set will include all treated patients who have at least 1 of the PK parameters of interest.

9.2.5. Immunogenicity Analysis Set

The Immunogenicity Analysis Set will include all treated Arm A patients who have at least 1 ADA sample collected.

9.2.6. Biomarker Analysis Set

The Biomarker Analysis Set will include all treated Arm A patients who have at least 1 baseline biomarker assessment performed.

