2. STUDY OBJECTIVES AND ENDPOINTS

2.1. Objectives

Primary Objective

To demonstrate the benefit of maintenance treatment with avelumab plus BSC vs. BSC alone in prolonging overall survival (OS) in patients with unresectable locally advanced or metastatic UC whose disease did not progress on or following completion of first-line platinum-containing chemotherapy in each co-primary UC patient population: 1) patients determined to have PD-L1-positive tumors (including infiltrating immune cells) by a verified GMP PD-L1 IHC test, and 2) all randomized patients.

Secondary Objectives

- To compare the PFS of avelumab plus BSC vs. BSC alone in patients determined to have PD-L1-positive tumors (including infiltrating immune cells) by a verified GMP PD-L1 IHC test, and in all randomized patients.
- To evaluate the anti-tumor activity of avelumab plus BSC and BSC alone according to Response Evaluation Criteria in Solid Tumors (RECIST) v1.1 in patients determined to have PD-L1-positive tumors (including infiltrating immune cells) by a verified GMP PD-L1 IHC test, and in all randomized patients.
- To evaluate the overall safety profile of avelumab plus BSC and BSC alone.
- To evaluate the PK of avelumab in each of the co-primary UC patient populations treated with avelumab.
- To assess the immunogenicity of avelumab in each of the co-primary UC patient populations treated with avelumab.
- To evaluate candidate predictive biomarkers of sensitivity or resistance to avelumab in pre-treatment tumor tissue in each of the co-primary UC patient populations treated with avelumab.
- To evaluate the effect of avelumab plus BSC and BSC alone on patient-reported outcomes (PROs) in each of the co-primary UC patient populations.

Exploratory Objectives

- To explore the predictive and/or pharmacodynamic (PD) characteristics of peripheral blood and additional tumor tissue biomarkers relevant to the mechanism of action of or resistance to avelumab.

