7.5.2. Peripheral Blood

Specimens will be retained as banked biospecimens (see Section 7.6) and will include whole blood, serum and plasma samples that will be retained in a biobank for exploratory assessments, unless prohibited by local regulation or by decision of the Institutional Review Board or Ethics Committee. Samples may be used to identify or characterize cells, DNA, RNA, or protein markers known or suspected to be of relevance to the mechanisms of action, or the development of resistance to study treatment. These include biomarkers that may aid in the identification of those patients who might preferentially benefit from treatment with avelumab plus BSC vs. BSC alone, including but not limited to biomarkers related to anti-tumor immune response or target modulation, such as soluble IL-8 or IFN γ , and/or tissue FoxP3, PD-1, PD-L2.

As per Protocol Amendment 6, following the final OS update, the collection of biomarkers will no longer be performed/collected.

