Because the observed incidence of ADA is highly dependent on multiple factors including the assays used for ADA detection, timing of sample collection, and immune status of the patients, the incidence of ADA observed in the planned study may differ from the incidence reported in historical clinical trials.

Analysis of Biomarker Endpoints

Analyses to evaluate candidate predictive biomarkers of sensitivity or resistance to avelumab in addition to PD-L1 expression defining the co-primary population may also be performed in which biomarker status (ie, positive or negative) will be determined in all randomized patients by a predictive biomarker test with an established scoring algorithm defining positive and negative that is developed by the sponsor. Analysis of primary and secondary efficacy endpoints in subgroups defined by biomarker status will be performed and reported as described above. Comparisons will be made between biomarker subgroups (positive and negative) within treatment arms and between treatment arms within biomarker subgroups.

Exposure/Response Analysis

In addition, the relationship between exposure and efficacy and safety endpoints may be explored, as necessary, based on emerging efficacy and safety data. Refer to the SAP for details. The results of these modeling analyses may be reported separately from the clinical study report.

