9.4.1. Statistical Analysis of Biomarker Endpoints

It is possible that, during the course of this study, emerging data and/or methods will suggest additional patient selection strategies beyond the verified GMP PD-L1 test used to define the co-primary populations. Retrospective analysis of biomarkers such as PD-L1 (using a different method from the GMP test) and CD8 are planned as a secondary objective to enable refinements in patient selection strategy, whether via technical modifications or revised thresholds. These methods may be single- or multi-analyte based on IHC or immunofluorescence. Further exploratory analyses may also be performed to assess the predictive and/or pharmacodynamic utility of additional methods, such as profiling of gene expression signatures indicative of immune activation. The Biomarker Analysis Set will be used for the analysis of biomarker endpoints.

Biomarkers will be assessed separately for whole blood, serum, plasma, archival tumor tissue, and de novo tumor biopsies. In each case, summaries of baseline levels, changes from baseline (where appropriate), gene alteration or biomarker signature status, will be reported. For continuous variables summary statistics may include the mean, ratio to baseline, standard deviation, median, 25th and 75th quartile, %CV and minimum/maximum levels of biomarker measures; for categorical variables, the summary may include number, percentage, and odds ratio, as appropriate.

Data from biomarker assays will be analyzed using graphical methods and descriptive statistics such as linear regression, t-test, and analysis of variance (ANOVA). The statistical approach may examine correlations of biomarker results with pharmacokinetic parameters and measures of anti-tumor efficacy.

Regarding exploratory biomarkers, the data analysis will be conducted with the goal of identifying predictive and/or pharmacodynamic (ie, baseline and change from baseline values) biomarkers associated with clinical outcome, encompassing both safety and efficacy. Candidate biomarkers will be validated in subsequent trials.

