4.3.3. Biomarker analysis set

The biomarker analysis set is a subset of the safety analysis set and will include patients who have at least one baseline biomarker assessment performed.

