6.2.5. Biomarker endpoints

Secondary endpoints in the study are candidate predictive biomarkers in tumor tissue including, but not limited to, PD-L1 expression and tumor infiltrating CD8+ T lymphocytes.

Exploratory endpoints in the study include peripheral blood and additional tumor tissue biomarkers consisting the levels of cells, deoxyribonucleic acid (DNA), ribonucleic acid (RNA), or proteins that may be related to anti-tumor immune response and/or response to or disease progression on avelumab, such as genes related to IFN- γ or transforming growth factor (TGF)- β .

Biomarker data will be analyzed based on the biomarker analysis sets as defined in [Section 4.3.3](#).

Biomarkers will be summarized at all timepoints described below:

- Blood biospecimens for exploratory assessments: C1D1, C1D15 (Arm A only), C2D1, C3D1, C5D1 and EOT.
- Tumor based biomarkers, archival FFPE Tumor Tissue Block: screening
- Tumor based biomarkers, de novo Tumor Biopsy: screening and End of Treatment.

Descriptive summary statistics (mean, SD, median, Q1, Q3, coefficient of variation, minimum, and maximum), at each timepoint and ratio to baseline at each visit (if appropriate) will be provided for avelumab for continuous variables. Non-continuous variables will be summarized using n/N and percent at each timepoint and treatment arm.

For each biomarker or set of biomarkers, patients may be classified as positive, negative, or some other category according to scoring algorithms and cut-offs established from external

sources. If no external standards exist, biomarkers may be stratified using the median: \leq median and $>$ median. Percent of patients in each category will be tabulated and tested using methods for categorical variables.

Biomarkers may be included as a covariate in a survival analysis model; biomarkers will be stratified on the above-mentioned classifications. Using a Cox proportional hazard model, HR, 95% CI, and p-values will be calculated for OS (primary endpoint) and PFS by BICR assessment (secondary endpoint). Further analyses may include the biomarker status by treatment arm interaction. If there are fewer than 20 events in a subgroup, or the HR is not estimable, only descriptive summary statistics will be provided.

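### Three different populations are named for the candidate predictive biomarkers and, PD-L1 status apart, the treatment-by-biomarker interaction is optional, so a purely prognostic marker could be carried forward as predictive

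*Protocol*

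**What the plan says.** The secondary objective in protocol 2.1 reads: "To evaluate candidate predictive biomarkers of sensitivity or resistance to avelumab in pre-treatment tumor tissue", and goes on to refer to each co-primary population treated with avelumab. SAP 2.1 repeats it. Protocol 7.5.2 states a comparative aim for marker work, to help identify "patients who might preferentially benefit from treatment with avelumab plus BSC vs. BSC alone". Protocol 9.4.1 says that CD8 and PD-L1 by other methods are studied so that patient selection can be refined.

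The population for this work is set in three places:

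- Protocol 9.2.6: "The Biomarker Analysis Set will include all treated Arm A patients who have at least 1 baseline biomarker assessment performed". Section 9.4.1 then applies it: "The Biomarker Analysis Set will be used for the analysis of biomarker endpoints".
- Protocol 9.3.2 opens by placing its analyses on the Full Analysis Set. Its biomarker paragraph, introduced as something that *may* be done, says marker status "will be determined in all randomized patients by a predictive biomarker test", and continues: "Comparisons will be made between biomarker subgroups (positive and negative) within treatment arms and between treatment arms within biomarker subgroups".
- SAP 4.3.3: "The biomarker analysis set is a subset of the safety analysis set and will include patients who have at least one baseline biomarker assessment performed". Under SAP 4.2 the safety set holds dosed Arm A patients and Arm B patients who completed Cycle 1 Day 1, so both arms are in it.

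On the model, SAP 6.2.5 says that a marker *may* enter a Cox model for OS and BICR PFS as a covariate, and adds: "Further analyses may include the biomarker status by treatment arm interaction". SAP 6.4 is firmer. For its listed subgroups, which include baseline PD-L1 status, it commits to a Wald test of treatment-by-subgroup interaction for OS and PFS on the FAS. CD8 and the other candidates are not on that list.

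**The concern.** A marker is predictive if the effect of avelumab plus BSC relative to BSC alone differs by marker level. It is prognostic if outcome differs by marker level whatever the treatment. Within one arm the two cannot be told apart. In a two-arm Cox model without an interaction, the marker coefficient averages over the arms and is again a prognostic quantity. Only the interaction, or the set of treatment HRs by marker level, addresses the objective.

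The documents leave open which patients are analysed and whether that term is fitted at all. The two-step rule in SAP 6.2.5 adds to the exposure, because second-step analyses are chosen from first-step results and a prognostic hit could be taken forward. At stake is the reading of a secondary objective that is meant to inform patient selection.

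**Working it through.** **1. The passages side by side**

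| Place | Patients | Can compare arms by marker? |
|---|---|---|
| Protocol 9.2.6, used in 9.4.1 | Treated, Arm A | No |
| Protocol 9.3.2 | All randomized | Yes, but optional and with no interaction test named |
| SAP 4.3.3, used in 6.2.5 | Treated, both arms | Yes, but the interaction is optional |
| SAP 6.4 (PD-L1 status) | FAS, both arms | Yes, interaction test committed |

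The first three differ from one another. Protocol 6.1.1 makes a recent tumor sample mandatory for all patients, so Arm B material exists.

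**2. The plan's own figures**

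Schoenfeld's formula with 1:1 allocation, one-sided, ignoring the interim look: power = Φ(|ln HR| × √(D/4) − z_α).

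- All patients (425 events, HR 0.70, α = 0.015): 0.3567 × 10.31 = 3.68; 3.68 − 2.17 = 1.51; power 93.4% (stated 93%).
- PD-L1-positive (219 events, HR 0.65, α = 0.01): 0.4308 × 7.40 = 3.19; 3.19 − 2.33 = 0.86; power 80.5% (stated 80%).

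The formula and event counts agree with the plan.

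**3. A purely prognostic marker, Arm A only**

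Assumptions not in the documents: 50% prevalence, the same marker HR in both arms (true interaction HR = 1), two-sided 0.05. About 190 of the 425 deaths are taken to fall in Arm A. The factor is √(190/4) = 6.89.

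| Prognostic HR | \|ln HR\| × 6.89 | minus 1.96 | P(significant) |
|---|---|---|---|
| 0.80 | 1.54 | −0.42 | 34% |
| 0.65 | 2.97 | 1.01 | 84% |
| 0.50 | 4.78 | 2.82 | 99.8% |

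**4. Simulation of the three possible analyses**

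The simulation used 668 patients, treatment HR 0.7, uniform accrual over 28 months, no drop-out, a cut at 425 events and 400 runs per row. Arm A deaths averaged 192 to 193.

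| Prognostic HR | Arm A only | Both arms, main effect | Both arms, interaction |
|---|---|---|---|
| 1.00 | 4.8% | 5.3% | 4.8% |
| 0.80 | 35% | 64% | 4.5% |
| 0.65 | 87% | 99.5% | 6.8% |
| 0.50 | 100% | 100% | 5.5% |

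The Monte Carlo standard error near 5% is √(0.05 × 0.95/400), or 1.1 points, so the last column is compatible with 5% throughout. Adding Arm B without the interaction does not help: the main-effect model flags the prognostic marker more often, because it has more events.

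**5. Power of the interaction test**

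With 1:1 allocation and 50% prevalence there are four cells of about D/4 events, so the variance of the log ratio of HRs is 4 × 4/D = 16/D. At D = 425, SE = √(16/425) = 0.194.

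| True ratio of HRs | \|ln\|/0.194 | Power, 425 events | Power, 315 events |
|---|---|---|---|
| 0.5 | 3.57 | 95% | 87% |
| 0.6 | 2.63 | 75% | 62% |
| 0.7 | 1.84 | 45% | 35% |
| 0.8 | 1.15 | 21% | 17% |

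The 315-event column is the planned minimum for the interim analysis, at which the protocol says the primary objective was met.

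**The case against.** Much can be said for the plan. Protocol section 9 allows the SAP to modify the protocol's analyses, and SAP 4.3.3 has both arms. Protocol 9.3.2 already places efficacy by marker on the FAS with between-arm comparisons, and the Arm A set is invoked only in 9.4.1, largely for levels, changes and correlations. PD-L1 status, a named secondary biomarker, gets a committed interaction test. For response by marker class, SAP 6.2.5 compares the arms with Fisher's exact test. The objective speaks of candidates in patients treated with avelumab, which explains the Arm A wording. Protocol 9.4.1 defers validation to later trials.

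Most of this stands, and it rules out some stronger readings. A reader might infer that biomarkers are to be analysed in Arm A only, but the SAP and protocol 9.3.2 say otherwise, so the Arm A limit is a conflict to resolve. A reader might infer that prognostic markers *would* be declared predictive, but no passage gives a criterion for predictive, and the covariate model is as optional as the interaction. Nor do the documents say that CD8 is prognostic. The safety-set basis is a minor matter: SAP 4.2 moves only Arm B patients who received avelumab in error, and it does so for safety analyses.

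Two things are not answered. The three populations remain unreconciled, and for markers other than PD-L1 status nothing commits the plan to the analysis that addresses the objective. The remark about later validation sits in the paragraph on exploratory biomarkers, while CD8 and PD-L1 by other methods are secondary.

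**Conclusion.** The point holds in a limited form. The documents give three incompatible populations for one objective, and for CD8 and other candidates the interaction is discretionary. A purely prognostic marker *could* therefore be carried forward as predictive. The size depends on the assumed prognostic strength. At HR 0.80 the chance of a significant result is already about 35% in Arm A and 64% in a two-arm main-effect model, against about 5% for the interaction test. These figures illustrate analyses the text permits; no document prescribes an Arm A OS comparison at two-sided 0.05. Prevalence, prognostic HRs, significance level, uniform accrual and absence of drop-out are assumptions. The effect is confined to the secondary and exploratory biomarker work. It merits correction, but it does not touch the primary OS tests.

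**What to change.** 1. Reconcile protocol 9.2.6 and 9.4.1 with 9.3.2, and carry the result into SAP 4.3.3. OS and BICR PFS by marker should use all randomized patients with a baseline tumor result, by randomized arm. Keep the treated set for descriptive and pharmacodynamic summaries. Deleting only the Arm A restriction is not enough, because the set would still be limited to treated patients. The objective's closing reference to patients treated with avelumab needs a matching clarification.
2. In SAP 6.2.5, make the Cox model with treatment, marker and treatment-by-marker interaction the stated analysis for candidate predictive markers, as SAP 6.4 does for PD-L1 status. Report the treatment HR with 95% CI at each marker level, and the interaction HR.
3. Label covariate-only and within-arm results as not separating prognostic from predictive effects.

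The cost is wording and one more model term per marker, on tissue already required. Intervals will be wider and fewer markers will look positive: power is about 75% for a ratio of HRs of 0.6 and 45% for 0.7 at 425 events, and lower with fewer events.
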